2.11.2 Procedure for unblinding if needed

There is no planned unblinding procedure in this trial since there is no known severe side effect of physical exercise that could lead to an emergency unblinding. The unblinded standard clinic care participants receive during the trial can deal with minor complaints caused by physical exercises, such as muscle soreness and fatigue.

2.12 Data collection and management

2.12.1 Plans for assessment and collection of outcomes

The outcomes will be collected at 3 months and 6 months after allocation. Considering the ongoing COVID-19 quarantine, we allow participants to finish the first outcome evaluation at 3 months \pm 4 weeks, and for the second outcome evaluation, 6 months \pm 4 weeks.

The research staff is required to receive a three-hour training session to ensure that they fully understand the protocol and standard procedures for the trial. The blinded physicians for evaluating the primary and secondary outcomes attend a one-hour training on the outcome assessment. All the research questionnaires and tests will be conducted at the Children's Hospital of Fudan University. Data will be collected with a case report form (CRF) and recorded in an ACCESS database. The description of study instruments is provided in the outcome part of this protocol. The demographic information of participants, including birth date, sex, height, weight, routine habit of exercise, and current drug use, are recorded on the CRF. The test record of CANTAB will be downloaded from the Cambridge cognition official website and automatically saved as an excel document. All data collected during the study will be kept in a locked room or protected research server. Back-ups in the study folder on this protected research server will be saved regularly (once per 3 months). Only the study team has access to these documents. To ensure this trial is applied consistently to high quality, the Clinical Trial Unit (CTU) of Children's Hospital of Fudan University will regularly monitor enrolment records, CRFs, informed consent, and data records.

The CRF will be double-entered into the ACCESS database by two investigators independently. The data will then be checked according to the correct range of values to ensure no erroneous entries. All missing data will also be checked and properly coded. Data monitoring and validation will be performed by the CTU of the Children's Hospital of Fudan University periodically. The CTU will preserve the original CRFs and all other study documents until 5 years after the last publication of this trial. The ACCESS database will record any changes to the raw data. For each time point, once all data have been inputted and checked, the database will be locked, and a data download request will be made so that only the authorized person gets access to the data. The data will be downloaded into SAS, R, and STATA formats for statistical analyses.

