2.6 Outcomes

2.6.1 Primary Outcome Measure:

Hyperactivity/Impulsivity score change in SNAP-IV clinician-rated scale. The Swanson, Nolan, and Pelham Questionnaire (SNAP-IV) Rating Scale is a revised version of the Swanson, Nolan, and Pelham (SNAP) Questionnaire that utilizes the DSM-IV criteria for ADHD and oppositional defiant

disorder, rated by caregivers or professionals[33,34]. It comprises three subscales: Inattention, Hyperactivity/Impulsivity, and Oppositional Defiant Disorder. The score of each item is rated with a 4-point Likert scale (0 = not at all, 3 = very much). The Chinese version of the SNAP-IV has good internal consistency ($\alpha = 0.95$) and test-retest reliability ($ICC = 0.68$), and its sensitivity and specificity for ADHD diagnosis are 0.87 and 0.79, respectively[35]. We ask the blinded clinician to rate the 9-item-Hyperactivity/Impulsivity subscale to evaluate change in ADHD Hyperactivity/Impulsivity symptoms in children. The Hyperactivity/Impulsivity subscale score is calculated by adding the 9 items; the score will range from 0 to 27. The change of score is calculated by the Hyperactivity/Impulsivity score at 3 months after enrollment (both the Baduanjin exercise group and Routine physical exercise group went through 3 months of intervention at this point) minus the Hyperactivity/Impulsivity score at baseline (enrollment).

2.6.2 Secondary Outcome Measure:

- (1) Change of Scoring evaluation of the TCM symptoms. The TCM symptom scale was developed from the guideline system for traditional Chinese medicine's new drug clinical research to evaluate the severity of TCM symptoms in children[36]. This scale includes 23 items; each presents one common TCM symptom. Each symptom is rated 1-4 points according to its severity by a trained researcher with extensive experience in TCM, using observation, auscultation and olfaction, inquiry, pulse feeling, and palpation. The total score is calculated by adding the scores of all 23 items. The change of score is calculated by TCM symptoms score after 3 months of enrollment (both the Baduanjin exercise group and Routine physical exercise group went through 3 months of intervention at this point) minus TCM symptoms score at baseline (enrollment).

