(5) Children's executive function is extrapolated by neuropsychological tests and ecological rating scales. The Cambridge neuropsychological test automated battery (CANTAB) is chosen to evaluate the executive function change after physical exercise. The CANTAB is a computer-based validated cognitive assessment system consisting of a battery of neuropsychological tests administered to participants using a touch screen computer[43]. This system provides accurate and sensitive computerized psychological testing. It aims to be culture and language-independent by using non-verbal stimuli in most tests suitable for school-age children and adolescents. The Motor Screening Task, Spatial Working Memory, Stop Signal Task, and Rapid Visual Information Processing are applied in this trial.

[figure not shown]
The ecological executive function of participants is assessed by the Behavior Rating Inventory of Executive Function, Second Edition (BRIEF-2). Originally developed by Gerard Gioia, this scale is an assessment of executive function behaviors at home for children and adolescents ages 5–18, mainly used to evaluate ADHD in children and has been shown to be superior to other rating systems as it taps into unique behaviors typically associated with the disorder[43]. This scale has nine different well-validated subscales and three indexes consistent with widely accepted theory: Behavior Regulation, Emotion Regulation, and Cognitive Regulation. This scale is translated into Chinese and has been proven to have convincing reliability and validity[44]. The performance change in CANTAB and BRIEF-2 will be compared between the two groups in this trial.

(6) Visual Perception of children is measured by the Developmental Test of Visual Perception-2nd edition (DTVP-2)[45]. It is a well-researched, norm-referenced measure of visual perception and visual-motor abilities in individuals ages 4 to 12. It has 8 subtests that measure different but interrelated visual-perceptual and visual-motor abilities along with 3 index scores--General Visual Perceptual Index, Motor-Reduced Visual Perception Index, and Visual-Motor Integration Index. The different visual perception performances will be tested before and after intervention and compared between groups.

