2.11 Assignment of interventions: Blinding

2.11.1 Who will be blinded

The standard clinic care will be given by a doctor who knows that the patient is participating in this trial but is unaware of the patient's study group. The primary and secondary outcomes investigator will also be unaware of the patient's grouping. One psychiatrist blind of allocation will talk with the family about their children's ADHD and ODD symptoms and rate it with the SNAP-IV scale. Another Chinese traditional medical doctor blind of grouping will evaluate the severity of traditional Chinese medicine symptoms of children and rate it with TCM symptom scale.

All researchers conducting outcome assessments will be masked in the trial. The trial statistician will also be blinded regarding the treatment code when he develops the statistical analysis plan and writes the statistical programs, which will be validated and completed using dummy randomization codes. The actual allocation will only be provided to the study team after locking the database.

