2.12.2 Plans to promote participant retention and complete follow-up

Before the beginning of the intervention, researchers and caregivers will discuss the best way to implement the exercise at home and strategies to encourage the child's participation. During the intervention, several actions were taken to engage parents and children of both groups in promoting physical exercise at home. Each family was invited to join a Wechat (a Chinese multi-purpose messaging and social media app) discussion group, where they can check their fitness tracker data with researchers daily. Children are given a set of toy coins and a money box on the day of consent signing. They can add one coin into the money box once their data are examined the next morning. Children are given a brochure containing a list of prizes and encouraged to choose gifts with values ranging from 15 to 90 coins. Gifts can be exchanged and sent to their home at any time during the intervention and within 2 months after the intervention. Furthermore, a handwritten, personally signed thank-you card from researchers is sent at the end of the first week of their intervention. Three designed medals—a bronze, a silver, and a golden- are awarded to the children at the end of each month of their intervention sequentially.

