#### *-Intent-to-Treat population*

Intent-to-treat (ITT) population will be defined at the moment the randomization is performed. This will be the primary analysis for the trial.

Participants will be excluded from the ITT analysis if the primary outcome is missing, forming a modified ITT population (mITT).

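### Outcome ratings have no remote fallback and no attendance-linked retention measure, although quarantine is expected and a missing 3-month score removes the child from the primary analysis

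*Protocol*

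**What the plan says.** **Where and when.** Protocol 2.12.1 places every assessment on site: "All the research questionnaires and tests will be conducted at the Children's Hospital of Fudan University". The same section acknowledges the pandemic: "Considering the ongoing COVID-19 quarantine, we allow participants to finish the first outcome evaluation at 3 months", with a tolerance of 4 weeks either side, and the same tolerance at 6 months. Neither document describes a telephone, video, postal or electronic alternative. Families may live in Shanghai, Zhejiang or Jiangsu (Protocol 2.2.1).

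**How outcomes are obtained.** For the primary outcome, Protocol 2.11.1 says: "One psychiatrist blind of allocation will talk with the family about their children's ADHD and ODD symptoms and rate it with the SNAP-IV scale". Table 1 in Protocol 2.7 lists several of the other scales as completed by the parent. Some outcomes need the child present. In Protocol 2.6 the TCM scale is rated "using observation, auscultation and olfaction, inquiry, pulse feeling, and palpation", CANTAB is "administered to participants using a touch screen computer", and DTVP-2 is a test that the child performs.

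**Retention.** Protocol 2.12.2 offers coins once a day's exercise data have been examined, a thank-you card after the first week, and a medal at the end of each intervention month. It adds: "Gifts can be exchanged and sent to their home at any time during the intervention and within 2 months after the intervention". None of these is conditional on coming to the 3-month or 6-month rating.

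**Consequences of a missing score.** SAP 4.2 states: "Participants will be excluded from the ITT analysis if the primary outcome is missing". The primary outcome is the 3-month change (Protocol 2.6.1, SAP 2.2.1), and the 6-month change is secondary (SAP 2.2.2). SAP 5.2.1 imputes baseline covariates only. Protocol 2.5 counts two consecutive weeks without exercise and without a reasonable cause as drop-out. It limits data recording to the period before drop-out, but keeps those data in the analysis.

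**The concern.** The plan foresees the obstacle that would keep families away, and its only answer is more time. A family still unable or unwilling to travel when the window closes loses the primary score, even though that score comes from a conversation with a blinded clinician. The retention section adds nothing specific to the visits. The child who has stopped exercising, plausibly the likeliest to miss a rating, earns no more coins and has no reward waiting at either visit.

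Two things are at stake. The first is power, because the 5% drop-out allowance in SAP 3.6 leaves little slack. The second is validity. Exclusion for a missing 3-month score happens after randomisation, so if missingness differs by arm and is related to adherence or response, the between-arm difference is biased in a way that the primary analysis cannot detect.

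**Working it through.** **1. Reproduce the sample size (SAP 3.6).** Inputs: difference 3.1, SD 5.8, two-sided 5%, 80% power, 1:1 allocation.
- Normal formula: n = 2 × (1.960 + 0.842)² × (5.8/3.1)² ≈ 55 per arm.
- Two-sample t-test: n = 55.93, so 56 per arm, as stated.
- Drop-out: 56/0.95 = 58.9, so 59 per arm or 118 in total. The plan rounds up to 120, or 60 per arm.

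**2. Margin for missing 3-month scores.** 120 − 2 × 56 = 8, and 8/120 = 6.7%, if the loss is evenly split.

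**3. Power under higher loss.** Analysed n per arm = 60 × (1 − loss); t-test power at 3.1/5.8. Loss above 5% is an assumption. The last column is 2 × (56/(1 − loss), rounded up).

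| Loss | Analysed per arm | Power | Total to randomise to keep 56 per arm |
|---|---|---|---|
| 0% | 60 | 82.7% | 112 |
| 5% (plan) | 57 | 80.8% | 118 |
| 10% | 54 | 78.6% | 126 |
| 15% | 51 | 76.2% | 132 |
| 20% | 48 | 73.6% | 140 |

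If remote rating recovered half the scores at 20% loss (assumed), net loss would be 10%. Power would rise from 73.6% to 78.6%, a gain of 5.0 points.

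**4. Illustrative bias.** Within an arm, the retained mean departs from the full mean by the loss fraction times the gap between lost and retained children. Assume 15% loss in controls, 5% in the Baduanjin arm, and a gap of 3 points in both. The bias in the difference is then (0.15 − 0.05) × 3 = 0.3 points in size, and 0.3/3.1 = 9.7% of the planned effect. All three inputs are assumed.

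**5. Reward timing, from allocation.** One month is 365.25/12/7 = 4.35 weeks.
- Gift exchange closes at 3 + 2 = 5 months, week 21.7.
- The 3-month window runs from week 9.0 to week 17.0, wholly before the closing date.
- The 6-month window opens at week 22.1; the nominal visit is at week 26.1.

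The lapse therefore concerns the 6-month visit only.

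**6. Which scores a remote option could rescue.** As described, the clinician SNAP-IV rating and the parent-completed forms need no examination or equipment. The TCM scale, CANTAB and DTVP-2 do need attendance and stay outside the remedy.

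**7. Drop-out rule against analysis set.** Take a child who meets a drop-out criterion before month 3. Protocol 2.5 keeps that child in the analysis with data up to drop-out. SAP 4.2 excludes the same child, because the 3-month score is missing. The two rules conflict, and the limit on recording means that an obtainable score may not be sought.

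**The case against.** The plan is not without protection:
- It allows an eight-week span for each rating.
- It restricts residence to three named areas and requires caregivers to be willing to attend follow-up (Protocol 2.2.1).
- It keeps daily WeChat contact (Protocol 2.5.1) and leaves the group open afterwards (Protocol 2.5.4).
- It defers additional sensory integration and behavioural therapy until the 3-month follow-up is complete (Protocol 2.5.3), which gives families a practical reason to attend.

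In addition, gifts remain exchangeable throughout the 3-month window, and the gap before the 6-month window opens is only about 2 days, which a slightly late start would close. No loss above 5% is documented, and the documents do not show that remote SNAP-IV rating is equivalent to rating in person. Video into the home could reveal the Kinect game. If poor adherers use the remote route more often, mode becomes mixed with adherence.

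Most of this stands as a limit on size. It does not supply a fallback when the window is missed or a measure tied to attendance. The unblinding and mode concerns shape the remedy; under SAP 4.2 the alternative is no score at all.

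A reader might infer three stronger things that the documents do not support:
- *That every reward depends on exercising.* Only the coins depend on exercise data; no exercise condition is stated for the card or medals.
- *That a missing 6-month score removes the child.* Protocol 1.2 mentions both months in its primary objective, but the primary outcome is fixed at 3 months, and the maximum-likelihood mixed model in SAP 5.1.1 can use a child with only the 3-month score.
- *That scores will be lost.* The documents establish a risk, not a rate.

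**Conclusion.** The point holds as a cheap improvement to the design. Ratings are tied to the hospital with only a date window as relief, no retention measure is linked to attending them, and a missing 3-month clinician score excludes the child from the primary analysis. More than 8 such losses in 120 leave fewer than the required 112.

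The power cost is moderate: about 1.4 points below the 80% target at 10% loss and 6.4 points below at 20%. These figures rest on the planned difference and SD, loss shared evenly between arms, and loss rates that the documents do not give. Bias from loss related to adherence is possible, but its size cannot be derived from the documents. Loss at 6 months affects the secondary question of whether the effect lasts, not the primary test.

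**What to change.** **Protocol 2.12.1.** Keep the hospital visit as the default. When a family cannot attend within the window, let the same blinded psychiatrist rate SNAP-IV by telephone, or by video with the family told not to mention or show the type of exercise or the equipment. Let caregivers complete the parent forms electronically. Record the mode on the CRF, and add to the SAP a repeat of the primary analysis without remote ratings. That repeat brings back the missingness which the fallback was meant to avoid, so read it as a check on mode, not as a better estimate.

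**Protocol 2.12.2.** Give a small fixed reward, identical in both arms, for completing the 3-month and the 6-month ratings whether or not the child kept exercising. Keep gift exchange open until the 6-month visit.

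**Protocol 2.5 and SAP 4.2.** State that outcome ratings are still sought after a child stops exercising or meets another drop-out criterion, unless the family withdraws from follow-up. Without this, the reward would not secure those scores. The drop-out criteria themselves need no change for this purpose. Reconcile the two sections on whether a child who drops out before month 3 is analysed.

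**Cost.** Protocol and SAP wording, one CRF field, small gifts and one sensitivity analysis, with no additional staff. The downside is a few ratings in a different mode and a small unblinding risk.

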2.12.2 Plans to promote participant retention and complete follow-up

Before the beginning of the intervention, researchers and caregivers will discuss the best way to implement the exercise at home and strategies to encourage the child's participation. During the intervention, several actions were taken to engage parents and children of both groups in promoting physical exercise at home. Each family was invited to join a Wechat (a Chinese multi-purpose messaging and social media app) discussion group, where they can check their fitness tracker data with researchers daily. Children are given a set of toy coins and a money box on the day of consent signing. They can add one coin into the money box once their data are examined the next morning. Children are given a brochure containing a list of prizes and encouraged to choose gifts with values ranging from 15 to 90 coins. Gifts can be exchanged and sent to their home at any time during the intervention and within 2 months after the intervention. Furthermore, a handwritten, personally signed thank-you card from researchers is sent at the end of the first week of their intervention. Three designed medals—a bronze, a silver, and a golden- are awarded to the children at the end of each month of their intervention sequentially.

2.13 Data management

Detailed information is displayed in the SAP

2.14 Confidentiality

Research data will be saved using a unique study identification code for each participant. The identification code list will only be approached by the research team during the study. It will be documented and safeguarded by the principal investigator according to ethical guidelines after the completion of the study. The data manager from the CTU will have access to the completed anonymous final dataset. No patient identification details will be reported in any published papers.

2.15 Statistical methods

2.15.1 Statistical methods for primary and secondary outcomes

The primary outcome is a continuous variable: Hyperactivity/Impulsivity score change in the SNAP-IV scale. The primary analysis will be based on the intention-to-treat (ITT) population. The generalized linear model (GLM) will be used to test the difference 3 months after allocation between the groups. The estimated means and two-sided 95% confidence intervals (CI) will be derived. All secondary outcomes will be analyzed for a superiority-designed trial and two-sided significance with alpha=5% and standard 95% CIs for the treatment differences in these outcomes between the two treatment groups. Secondary outcome analyses will be based on the ITT population unless specified. SAS (version 9.4) will be used to perform all data analyses and generate the majority of data displays. STATA® (version 16.0) or SPSS, S-Plus, or R may also be used for data analyses and for generating statistical graphs. The other outcome measures will be calculated and presented with the same method of primary and secondary outcomes. Continuous variables will be summarized according to the number of subjects with non-missing data (n), mean, standard deviation (SD), median, minimum, maximum, and range interquartile (IQR). The confidence intervals will be reported on summaries of continuous effectiveness variables. Categorical variables will be summarized according to the absolute frequency and percentage of subjects (%) in each category level. The denominator for the percentages is the number of subjects in the treatment arm with data available unless noted otherwise.

Detailed information is displayed in the SAP.

2.15.2 Plans to give access to the complete protocol, participant-level data, and statistical code

The datasets used and analyzed during this trial can be granted access by the corresponding author and the safety monitoring board(DSMB) of CTU upon reasonable written request.

3 Oversight and monitoring

3.1 Composition of the coordinating center and trial steering committee

This monocenter-designed study is performed and coordinated at the Children's Hospital of Fudan University. Daily support is provided by:

Principle investigator: supervises the trial and takes medical responsibility for the patients.

Data manager: organizes data collection and analysis and safeguards quality and data.

Study physician: trial registration, identifies potential recruits, performs outcome measures, takes informed consent, ensures follow-up according to protocol annual safety reports.

Study therapist: performs outcome measures, coordinates study visits, and daily follow-up of participants.

The study team meets weekly. There is no trial steering committee or stakeholder and public involvement group.

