### **3.5. Blinding**

The physicians in charge of outcome evaluation will be blinded about the grouping of the patients. The trial statistician will also be blinded regarding the treatment code when he develops the statistical analysis plan and writes the statistical programs, which will be validated and completed using dummy randomization codes. The actual allocation will only be provided to the study team after lock of the database.

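### Do the therapist's combined duties and the database-lock sentence leave CANTAB and DTVP-2 without masked testers?

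*Protocol*

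**What the plan says.** **General masking.** Protocol 2.11.1 states: "All researchers conducting outcome assessments will be masked in the trial". It adds that the investigator of the primary and secondary outcomes does not know the child's group. SAP 3.5 is narrower and speaks of physicians: "The physicians in charge of outcome evaluation will be blinded about the grouping of the patients".

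**Named raters.** Protocol 2.11.1 identifies two by role. For the clinician-rated SNAP-IV: "One psychiatrist blind of allocation will talk with the family". For the TCM symptom scale: "Another Chinese traditional medical doctor blind of grouping will evaluate the severity".

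**Lock sentence.** Protocol 2.11.1: "The actual allocation will only be provided to the study team after locking the database". SAP 3.5 says almost the same: "The actual allocation will only be provided to the study team after lock of the database". In both places it directly follows the statement that the statistician's programs are validated with dummy codes.

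**Roles.** Protocol 3.1: "Study therapist: performs outcome measures, coordinates study visits, and daily follow-up of participants". The study physician's entry in the same list includes both consent and outcome measures.

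**Who learns the arm.** Investigators or researchers open the envelopes (Protocol 2.10.2 and 2.10.3). A physician is present while a nurse records the allocation (SAP 3.4). Researchers help install the Baduanjin equipment and check its uploads (Protocol 2.4.2 and 2.5.1).

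**CANTAB and DTVP-2.** Protocol Table 1 marks both as completed by the child. No section names the person who gives them.

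**The concern.** Families know their arm, so for tests given by staff the masking of the tester is the main protection against measurement bias. A tester who knows the arm can prompt, encourage or explain differently.

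Three features suggest that this protection might fail. First, the lock sentence cannot be literally true of everyone on the study team, since some of them open envelopes and monitor software that only one arm uses. Second, the role list gives the therapist both outcome measurement and daily contact, and the daily contact described elsewhere in the protocol includes checks of uploaded exercise data. Third, the two instruments with named masked raters are SNAP-IV and the TCM scale; CANTAB and DTVP-2 have none, and the SAP's blinding section mentions only physicians, so it does not reach a therapist.

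At stake would be two of the SAP's secondary outcomes, one of which (CANTAB) also feeds the mediation analysis in Protocol 1.2. A trial report that repeated both masking sentences might also claim more than was done.

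**Working it through.** No figure in the plan bears on this point, so the check sets the sections side by side and counts what is exposed.

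**1. How much of the assessment schedule lacks a named masked rater?** Protocol Table 1 has 10 assessment rows:

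| Type | Rows | Count |
|---|---|---|
| Named masked rater | SNAP-IV hyperactivity/impulsivity; TCM; SNAP-IV inattention/ODD (clinician part) | 3 |
| Family questionnaire | WFIRS, CBCL, SDQ, BRIEF-2, Child Sensory Integration Checklist | 5 |
| Test with no named tester | CANTAB, DTVP-2 | 2 |

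3 + 5 + 2 = 10. The question concerns 2 rows, which are items 9 and 11 of the 12 secondary outcomes in SAP 2.2.2. For DTVP-2 that is 1 row × 2 visits = 2 comparisons by SAP Table 3, or 3 indexes × 2 visits = 6 by the SAP variable list. CANTAB comparisons cannot be counted, because it appears in neither SAP Tables 2–3 nor the variable list.

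**2. Do the masking rules reach those 2 rows?** Yes, by two routes. The rule for all outcome assessors in Protocol 2.11.1 has no exception. The sentence on the investigator of primary and secondary outcomes applies too, because Protocol 2.6.2 (items 5 and 6) and SAP 2.2.2 both class the tests as secondary. Table 1 puts them under a separate heading for other measures, which clouds the second route but not the first. Its child-completed label says who does the test and nothing about who is masked.

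**3. Does the role list contradict the rule?** Only if one person follows up and tests the same child. Protocol 3.1 does not say so, and it does not define daily follow-up. The upload checks are assigned to researchers, not to the therapist by name. The physician's consent duty does not reveal the arm, because consent comes before the envelope is opened. SAP 3.4 does let a physician see the allocation, but nothing says that this physician later tests the child. Protocol 3.3 refers to physicians and therapists in the plural, so duties can be divided within the existing team.

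**4. What does the lock sentence mean?** It speaks of the actual allocation immediately after a sentence about dummy codes. The natural contrast is between dummy and real codes, so the subject is release of the real code for analysis. The reading that nobody on the team knows any child's arm is ruled out by Protocol 2.10.

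**5. Which lock?** Protocol 2.12.1 locks the data at each time point, which on its own might allow release after the 3-month lock. SAP 4.3 closes data collection when the last patient completes the 6-month follow-up, and SAP 4.5 locks once all data are in and checked. Together these point to the final lock.

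**6. Are the smaller mismatches real?** Protocol 2.10 speaks of investigators and researchers, SAP 3.4 of a trained physician with a nurse. These are compatible: the SAP adds detail. One contradiction is plain. Protocol 2.11.1 says "The standard clinic care will be given by a doctor who knows that the patient is participating in this trial but is unaware of" the study group, while Protocol 2.11.2 calls the same clinic care unblinded. It concerns care, and changes no outcome measurement or analysis.

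**7. Could a change still act?** Conduct was planned to March 2022 and SAP 2.0 is dated October 25, 2022. From March 31 that is 183 days to the end of September plus 25, or 208 days, about 7 months. If the schedule held, visits were over and only wording could change.

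**The case for a change.** The strongest case for a change is that a masking statement without a mechanism is only an assertion. The documents show several ways for staff to learn the arm, the team meets weekly with no stated split between masked and unmasked members, and the one list that assigns outcome testing pairs it with follow-up. SAP 3.5 could easily have covered all assessors and does not. DTVP-2 also lacks the protection that CANTAB has from computer delivery and automatically saved records.

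Part of this stands. The documents do not name who gives CANTAB and DTVP-2 or say how that person is kept from learning the arm, the lock sentence is loosely worded, and the two statements on clinic care disagree. What does not stand is the step from there to insecure masking. The SAP's narrower sentence does not repeal the protocol's general one, and that the therapist or an arm-aware physician gives the tests is an inference that no section supports.

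**Conclusion.** The concern does not call for a change. The plan already contains the rule that matters, and following it makes the CANTAB and DTVP-2 testers masked. What is missing is operational detail of a kind that a trial team normally settles in its delegation of duties. The clinic-care contradiction is a clerical slip with no effect on the data.

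The extent is 2 of 10 assessment rows, and mainly DTVP-2, since CANTAB leaves a tester less influence. The primary outcome and the TCM scale have named masked raters. Any bias cannot be sized, because the documents give neither the testers' identity nor a standard deviation for either test.

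This rests on two assumptions: that the general masking rule was followed, and that the lock sentence means release of the real code for analysis after the 6-month data are complete. If testers did know the arm, that would be a departure from the plan to disclose in the trial report, along with who gave the tests. Rewording the plan would not change what was measured or how it is analysed.
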